## **2.2. Pooling Algorithm for Analysis Centers**

Not planned, subgroups analyses by region are described in section 2.4.

## **2.3. Analysis Sets**

### **2.3.1. Full Analysis Set**

The Full Analysis Set (FA) will consist of all subjects who were randomized and who received at least one dose of study vaccine. This will be the primary population for all analyses (except immunogenicity, see below) described in this document.

### **2.3.2. Per-Protocol Immunogenicity Analysis Set**

The per protocol immunogenicity (PPI) population consists of all subjects who have received at least the first three vaccinations, according to the protocol-specified vaccination schedule (+/- 2 weeks), have at least one measured post-dose blood sample collected and were not diagnosed with HIV during the study. Samples taken after Week 48 from subjects in the PPI population who missed the 4th vaccination or did not receive the 4th vaccination in the protocol-specified time window (+/- 2 weeks) will be excluded from the analysis.

The analysis of the immune responses will be performed on the per protocol immunogenicity population.

### **2.3.3. Late Boost Analysis Set**

The Late Boost (LB) population consists of all subjects from per protocol immunogenicity analysis set who received the late boost vaccination (at least one of the two injections administered at the late boost visit).

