Subjects enrolled in the LTE phase will be offered participation in an extension to the LTE phase to investigate the safety and immunogenicity of a late boost vaccination approximately 3 years after the last vaccination in the main study (depending on availability of IRB and HA approvals per country/site regulations). Assessment of participants' eligibility for the late boost vaccination and vaccination itself will occur within 4 weeks prior to Week 192 until 4 months after Week 192 (Visit 22a, which can be split over several visits). Eligible, consenting subjects will be randomly assigned (3:1 ratio, see Table 2 below) in a blinded fashion to active vaccination with Ad26.Mos4.HIV and bivalent gp140 (Group 1b) or placebo (0.9% saline) (Group 2b). The aim is to have at least 48 participants enrolled in the late boost extension. Randomization will be stratified by region (USA, East Africa: assuming sufficient numbers from Rwanda in the LTE phase) and by group randomized to in the main study (Group 1/Group 2). Upon receipt of the late boost vaccination, participants will be followed up for immunogenicity and safety for a further 12 months or, if they consent to longer follow-up, 24 months. Unblinded interim data analysis (sponsor unblinding only) will be performed approximately 4 weeks after the last subject received the late boost vaccination. LTE subjects declining participation or not eligible for participation in the late boost extension will complete the study at Visit 23 of the LTE phase.

The duration of the subject's participation will be approximately 78 weeks (6-week screening + 72 weeks main study) for subjects not participating in the LTE phase and approximately 222 weeks for subjects participating in the LTE phase but not receiving a late boost vaccination and approximately 246 (12-month follow-up) or 294 (24-month follow-up) weeks for subjects receiving a late boost vaccination.

After vaccination, subjects will remain under observation at the study site for at least 30 minutes for presence of any acute reactions and solicited events. In addition, subjects will record solicited events in a diary for 7 days post-vaccination as described in Section 9.1.1. See Section 12.1.3 for grading of severity of solicited AEs. From the time of local regulatory approval of protocol amendment 5 onwards, TTS is considered to be an AESI. Thrombotic events and/or

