4.4. Inclusion and Exclusion Criteria for the Long-term Extension Phase

Each potential subject must satisfy all of the following inclusion criteria to be enrolled in the LTE phase of the study upon completion of the final main study visit at Week 72.

- 1. Each subject must sign an ICF appendix for the LTE phase indicating that he or she understands the purpose of and procedures required for the LTE phase and is voluntarily willing to participate in the LTE phase of the study.
- 2. Subject must be randomized to Group 1 or Group 2 of the main study.
 - Note: Upon sponsor unblinding at the Week 28 analysis, subjects randomized to Group 1 or Group 2 who have received all 4 vaccinations, will be asked to participate in the LTE phase and sign the ICF appendix for the LTE phase at Week 72. Subjects who attend their Week 72 visit prior to the sponsor's unblinding at the Week 28 analysis, will be enrolled in the LTE phase if they consent and sign the ICF appendix for the LTE phase and meet the eligibility criteria for the LTE phase. When the Week 28 sponsor unblinding subsequently occurs, subjects that started the LTE phase but turn out to have received placebo in the main study will be withdrawn from the LTE phase.
- 3. Subject must have received all 4 vaccinations of the main study.
- 4. Subject must be negative for HIV infection at the final main study visit at Week 72.
- 5. Subject must be willing/able to adhere to the prohibitions and restrictions for the LTE phase, as specified in the protocol and study procedures.

Any potential subject who meets any of the following exclusion criteria at the end of the main study will be excluded from participating in the LTE phase of the study.

- 1. Subject has any condition for which, in the opinion of the investigator, participation would not be in the best interest of the subject (eg, compromise the well-being) or that could prevent, limit, or confound the protocol-specified assessments.
- 2. Subject is planning to participate in an interventional study during the LTE phase, concerning studies with investigational HIV vaccines or other investigational HIV prevention which could be determined to interfere with HIV vaccine response in this study (ie, CD4-Ig depleting Env-specific Abs), which are disallowed.

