11.2. Analysis Populations

The safety population will consist of all subjects who received at least one dose of study vaccine, and for whom any post-dose data is available.

The immunogenicity population will consist of all subjects who received at least one dose of study vaccine, and who have immunogenicity data from at least one evaluable post-dose blood sample.

The per protocol immunogenicity population will consist of all randomized and vaccinated subjects for whom immunogenicity data are available, excluding subject samples with major protocol deviations expecting to impact the immunogenicity outcomes (for example missed vaccinations, natural infections, etc).

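### For immunogenicity, the Late Boost set inherits main-study per-protocol exclusions, so an HIV diagnosis at any time after the Week 192 re-randomisation removes a boosted subject completely

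*SAP*

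**What the plan says.** - **Late Boost set (SAP 2.3.3).** It consists of "all subjects from per protocol immunogenicity analysis set who received the late boost vaccination". Receiving "at least one of the two injections administered at the late boost visit" is enough, and there is no test of the boost window.
- **Parent set (SAP 2.3.2).** Subjects in the per-protocol immunogenicity (PPI) set must "have received at least the first three vaccinations, according to the protocol-specified vaccination schedule (+/- 2 weeks") and must be those who "were not diagnosed with HIV during the study". Both conditions apply to the whole subject. A further rule applies to samples: those taken after Week 48 from a subject who missed the fourth dose, or did not receive the fourth "vaccination in the protocol-specified time window (+/- 2 weeks) will be excluded from the analysis".
- **Use of the sets.** SAP 6.1 places immunogenicity on the PPI set and applies the main-study rules to late-boost data. SAP 5 places safety on the Full Analysis Set.
- **Entry to the boost.** For the long-term extension, Protocol 4.4 states "Subject must have received all 4 vaccinations of the main study", with no timing test. Protocol 4.5 then requires extension enrolment and HIV negativity.
- **Protocol per-protocol definition (11.2).** It works by "excluding subject samples with major protocol deviations expecting to impact the immunogenicity outcomes", and gives missed vaccinations and natural infections as examples.
- **Follow-up after infection (Protocol 12.3.3.1).** Subjects with confirmed HIV infection stay in safety and immunogenicity follow-up.

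**The concern.** The late boost is a new 3:1 randomisation with its own eligibility rules, but its immunogenicity population is filtered by rules written for the main study.

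The HIV condition matters most. Everyone is HIV negative at boost entry, so the condition can remove a boosted subject only for a diagnosis made after the new randomisation. It then removes that subject's samples from before infection too. If infection is related to arm or to immune response, the remaining arms are no longer the randomised ones. It also makes results unstable over time. A subject diagnosed between the interim analysis (about 4 weeks after the last boost, Protocol 11.6) and the final analysis would count in the first and vanish from the second, which would change the Week 196 estimates retrospectively.

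The timing rules raise a lesser issue: subjects or samples may be lost from a small comparison because of doses given about three years before the boost.

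No other set covers the gap. The broader immunogenicity population of Protocol 11.2 is not carried into the SAP, and SAP 2.3.1 makes the Full Analysis Set primary for everything except immunogenicity.

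**Working it through.** **1. Eligibility against analysis set**

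| Condition | To be randomised and boosted | To be analysed for boost immunogenicity |
|---|---|---|
| Doses 1–3 | Received | Received on schedule (+/- 2 weeks), or the subject is out |
| Dose 4 | Received | On schedule (+/- 2 weeks), or all samples after Week 48 are out |
| HIV | Negative at entry | No diagnosis during the whole study, or the subject is out |

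A subject can satisfy the middle column and fail the right-hand one. With a mistimed dose 4, the subject nominally stays in the Late Boost set but contributes no boost-phase sample.

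**2. Timing of each condition relative to the boost randomisation (Week 192)**

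- Doses 1, 2 and 3: 192 − 0 = 192 weeks, 192 − 12 = 180 weeks and 192 − 24 = 168 weeks before.
- Dose 4: 192 − 48 = 144 weeks before.
- HIV: 240 − 192 = 48 weeks after, or 288 − 192 = 96 weeks after with the optional longer follow-up.

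Dose timing is fixed before randomisation, so conditioning on it cannot bias boost versus placebo. HIV diagnosis comes after randomisation, so conditioning on it can.

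**3. How often the timing rules could apply**

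Protocol 6 and 9.1.2 give a window of −1/+3 weeks for doses 2 to 4. A dose that misses its window should not be given, apart from case-by-case exceptions. The effect therefore depends on what +/- 2 weeks means.

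- *Added to the protocol window*, as SAP 4.4 suggests: −1 − 2 = −3 weeks to +3 + 2 = +5 weeks. This is looser than the protocol and removes almost nobody.
- *Around the planned date:* −2 to +2 weeks. A protocol-compliant dose at +2 to +3 weeks then fails.

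SAP 2.3.2 does not say which applies.

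**4. Size, as illustration**

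The main-study figure comes first. Protocol 11.3 gives 90 versus 22 evaluable subjects, SD 0.4 log10, two-sided 5% and 80% power for 1.85-fold.

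- SE = 0.4 × √(1/90 + 1/22) = 0.0951.
- Detectable fold = 10^((1.960 + 0.842) × 0.0951) = 1.85.
- Power at 1.85-fold is 80.2% by the normal approximation and 79.5% by noncentral t. The stated figure reproduces.

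The protocol sets only a minimum for the boost: "The aim is to have at least 48 participants enrolled in the late boost extension". At 3:1 this is 48 × 3/4 = 36 active and 48 × 1/4 = 12 placebo. The same SD is assumed, and the difference is solved for 80% power with noncentral t on n1 + n2 − 2 degrees of freedom:

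| Subjects | Assumed loss | SE (log10) | Detectable fold |
|---|---|---|---|
| 36 vs 12 | none | 0.1333 | 2.41 |
| 32 vs 11 | about 10% | 0.1398 | 2.52 |
| 29 vs 10 | about 20% | 0.1467 | 2.64 |

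The normal approximation gives 2.36 for 36 versus 12. The documents state no power figure for the boost, and the loss fractions are not theirs.

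**The case against.** **The timing rules may be nearly empty.** Out-of-window doses should not have been given, and boosted subjects must have received all four doses. If the 2 weeks extend the −1/+3 week window, hardly anyone fails. Requiring a correctly delivered primary series is also a defensible per-protocol choice, since one late-boost objective compares matched with closely related priming. This stands. What remains is a possible loss of precision and an ambiguity to settle.

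**The HIV rule may never apply.** Subjects are selected as low risk, and Protocol 1.1.2.2 reports no HIV infections in the Week 72 analysis. That makes removals unlikely, but it says nothing about the later period that this SAP covers. The rule's form is wrong however rarely it applies.

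**The protocol itself names natural infections as grounds for exclusion.** True, but it excludes samples. Removing the whole subject is the SAP's addition.

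**Little formal inference depends on this set.** No formal hypothesis is tested, and SAP 6.3 specifies no boost-versus-placebo test. The late-boost immunogenicity objectives are secondary or exploratory, and the primary late-boost objective is safety. This limits the weight of the point and makes the detectable-fold figures illustrative only.

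**Stronger readings the documents do not support.** A reader might infer that boosted subjects are dropped from the trial's results altogether; safety keeps them. A reader might infer that 10% to 20% are lost; no count is given. A reader might infer that early dose timing biases the boost comparison; it was fixed before that randomisation.

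**Conclusion.** The point holds for immunogenicity only. The HIV condition is the substantive defect. It conditions a randomised comparison on a later event, discards valid pre-infection samples, and departs from the protocol's sample-level rule. The direction and size of any bias cannot be derived from the documents, and without post-boost infections there is none.

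The timing conditions are a lesser matter of precision. The number affected is unknown and probably small, unless +/- 2 weeks is read around the planned date. The illustrative move from 2.41-fold to 2.52-fold or 2.64-fold rests on the minimum enrolment of 48, an SD of 0.4 log10 carried over from the main study, and assumed losses. It should not be read as an expected loss.

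The change is worth making because the late-boost analyses are a stated purpose of this SAP and the remedy is a matter of wording.

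**What to change.** 1. Define the Late Boost immunogenicity set as all subjects randomised and vaccinated at the late boost with at least one post-boost sample, analysed by randomised arm, without requiring PPI membership. Name this set in SAP 6, where it is not mentioned now.
2. For subjects with HIV infection, exclude only samples taken after the last HIV-negative test. Starting the exclusion at the first positive sample would be too late. The late-boost schedule and Protocol 9.1.10 place post-boost HIV testing at Visits 23a, 24 and 25 only, so samples drawn between the last negative and first positive test may already follow infection. Protocol 9.3 and 12.3.3.1 instead imply testing at every post-boost visit, and the SAP should say which testing record it relies on.
3. Keep the PPI-nested set as a sensitivity analysis, so that the effect of the timing rules can be seen.
4. State in SAP 2.3.2 that the 2-week allowance is added to the −1/+3 week protocol window, consistent with SAP 4.4.

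The cost is SAP wording and one extra set of immunogenicity outputs for the sensitivity analysis. No new data collection is needed. Under the visit schedule, a subject first positive at Visit 23a and last negative on the boost day would still lose the samples in between. That is the price of keeping out possible post-infection responses.

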## **2.4. Definition of Subgroups**

The following subgroups will be investigated for the most relevant immunogenicity assays (more details in section 6.3):

- Region (Africa, USA)
- Ad26 VNA at baseline (<LLOQ, >=LLOQ)
- Sex (Female, Male)

- Race (Caucasian, Black or African American, Asian, Othera)
- BMI [ $<18.5$ ;  $18.5-<25$ ;  $25-<30$ ;  $\geq 30$ ]

### 3. INTERIM ANALYSIS AND DATA REVIEW COMMITTEE

A Data Review Committee (DRC) was planned to specifically review safety data (solicited and unsolicited AEs, SAEs, and available laboratory assessments) at 2 time points following injections of Mosaic gp140:

- Review blinded safety data (2 weeks of follow-up) after approximately 25 (15%) of subjects have received their third injection.
- Review blinded safety data (2 weeks of follow-up) after approximately 50 (30%) of subjects have received their third injection.

These analyses are described in a separate DRC Charter.

### 4. SUBJECT INFORMATION

Subject information will be analyzed based on the FA analysis set unless otherwise specified.

Continuous variables will be summarized using the following statistics, as appropriate: number of observations, arithmetic mean (mean), 95% confidence interval (CI) for the mean, standard deviation (SD), standard error (SE), median, quartiles (Q1 and Q3), minimum and maximum. The minimum and maximum will be presented to the same number of decimal places as the original data. The mean and median will be rounded to one more decimal place than the original data, while the SD, SE and 95% CI to two more decimal places.

#### 4.1. Demographics and Baseline Characteristics

The following demographic and baseline characteristics will be summarized.

- Sex (Female/Male)
- Age (years)
- Race
- Ethnicity
- Region
- Country
- Height (cm)
- Weight (kg)
- BMI ( $\text{kg}/\text{m}^2$ ), calculated from the recording of baseline height and weight.

#### 4.2. Disposition Information

Number and percentage of subjects that were 1) screened, 2) screening failures, 3) subjects meeting eligibility criteria but not randomized, 4) randomized and vaccinated, 5) randomized not vaccinated and 6) vaccinated but not randomized will be tabulated.

Number and percentage of subjects that completed and those who discontinued together with the reason(s) for discontinuation will be tabulated. This will be done for completion/vaccine discontinuation from further vaccination and from the trial.

---

a Subgroup “Other” should contain all remaining categories: Other, Multiple, American Indian or Alaska Native, etc.

The subjects receiving the late boost vaccination will also be presented split by the regimen they received for the prior 4 vaccinations.

#### 4.3. Concomitant Medications

The analysis of concomitant medications will be using the WHO drug dictionary as provided in the clinical database.

Based on their start and stop date, concomitant therapies will be reported in each period during which they were applied.

If a concomitant therapy record misses components of its start and/or stop dates (Day and/or month and/or year):

- In case of partial start or stop dates, the concomitant therapy records will be allocated to periods using the available partial information, without imputations. If, for example, only month and year are available, these will be compared to the month and the year of the periods, and the concomitant therapy record will be allocated to the period(s) where these date parts match.
- In case of a completely missing start date, the concomitant therapy will be considered as having started before the trial.
- In case of a completely missing end date, the concomitant therapy will be considered as ongoing at the end of the trial/cut-off date.

Concomitant therapies will be tabulated by post-dose phase. There will be special attention to Acetaminophen, NSAIDs or Antihistamines to identify medication that can mask local or systemic solicited events in the 8 days after the vaccinations and to systemic glucocorticosteroids during the whole study duration for possible influence on the immunogenicity results. Systemic glucocorticosteroids will be flagged in the overall CM listing. Subjects taking PrEP during the study will be listed.

Concomitant medication taken during the LTE will be listed.

#### 4.4. Exposure

Number and percentage of subjects by number of received vaccinations will be tabulated.

Tabulation of vaccine administered within and outside the protocol-specified time windows (-1/+3 weeks of the planned vaccination and additional 2 weeks, late boost: -4 weeks/+4 months) will be provided as well.

#### 4.5. Protocol Deviations

All major protocol deviations will be listed.

#### 4.6. Medical History

Medical history data will be listed. Listing will not be repeated for the late boost analysis.

### 5. SAFETY

The safety and tolerability endpoints are:

- Unsolicited AEs 28 days following each vaccination
- Solicited local and systemic AEs (reactogenicity), collected daily from day of vaccination for 7 days post-vaccination (day of vaccination and the subsequent 7 days).

The safety and tolerability analysis will be performed on the FA set. Specifically, the analysis for solicited adverse events will be done on those subjects in the FA set for whom reactogenicity assessments are available in the database (either via on-site assessments or via the diary pages of the CRF).

Safety data will be tabulated per period by regimen. Only the active periods will be shown in the tables (AE, Lab, VS), except for SAEs. In addition, for a selection of tables (AE, Lab), tabulations per subject by vaccine and per dose by vaccine will be provided.

For the subject receiving the late boost vaccination, the AEs will be tabulated as follows:

- Reporting only the late boost period (post-dose 5) for the 2 LB regimens (LB Tetravalent Clade C-Mos and LB Placebo)
- Reporting all post doses (post-dose 1,2,3,4,5) for the vaccine they received (Any post-dose will not be included).

In the ‘per subject by vaccine’ analysis, the safety will be presented per periods (post-dose 1, 2, 3, 4) by vaccine rather than by regimen. A ‘post any dose’ period (= regimen phase in section 2.1) will be added, that summarizes the safety after all administered doses of a vaccine. The post-any-dose period allows determining how many subjects reported events after administration of a certain vaccine regardless the number of doses. Each subject is counted only once. In case a subject has the same event after more than one dose, it is counted only once (and in case of showing attributes, the worst corresponding attribute is shown) in the post-any dose period. The denominator is the number of subjects that received the considered vaccine in the considered period.

In the ‘per dose by vaccine’ analysis, the safety will also be presented by vaccine. This table allows determining the incidence of events per administered dose of a certain vaccine. For example, if a subject has the same event at least once after dose 1 and at least once after dose 2 of the same vaccine, it is counted 2 times (so the numerator is the sum of post-dose 1, 2, 3 and 4 events in the “per subject by vaccine” table). In case of showing attributes, the worst corresponding attribute of each period are shown. The denominator is the total number of doses administered of the considered vaccine over all subjects.

At the 3th and 4th vaccination timepoint and the late boost timepoint, two vaccines should be administered at two different injection sites (left/right deltoid). The local solicited events should be linked to the medication injected in that specific injection site. However, for some subjects the link between local AE and injection site might be unavailable, so the AE will be attributed to both medications received by the subject (e.g. if a subject receiving Ad26 + gp140 HD with AE “Erythema”: Erythema will be counted for Ad26 and for gp140 HD). Systemic solicited and unsolicited AE will be reported under both the administered medications.

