^b Subjects will be divided into three groups: the first 20 enrolled subjects will have the Visit 22b 7 days post late boost, the next 20 enrolled subjects 3 days post late boost and the remainder of the subjects 14 days post late boost.

	Objectives		Endpoints
•	To explore the role of Ad26 neutralizing antibodies on the immune response to a late boost vaccination.	•	Ad26 neutralizing antibodies at the time of vaccination relative to the immune response as evaluated by ELISA.
•	To compare the immune response to late boost vaccination with a vaccine matched to the primary vaccination series (Group 2) vs a closely related vaccine (Group 1).	•	Relative ELISA magnitudes between groups randomized to Group 1 vs Group 2 in the main study.
•	To evaluate whether humoral responses induced by a late boost vaccination are able to mediate protection in non-clinical passive transfer studies.	•	Analysis of protection against HIV-related challenge viruses, such as simian human immunodeficiency virus (SHIV), in a suitable animal model, and/or in vitro.

Hypothesis

No formal statistical hypothesis will be tested. The proposed clinical study in healthy HIV uninfected subjects will evaluate the safety/tolerability and the immunogenicity of 2 different prime/boost regimens: priming with Ad26.Mos4.HIV and boosting with Ad26.Mos4.HIV and either Clade C gp140 plus adjuvant or a combination of Clade C and Mosaic gp140 plus adjuvant.

OVERVIEW OF STUDY DESIGN

This is a randomized, double-blind, placebo-controlled, parallel-group, multicenter, Phase 1/2a study in healthy HIV-uninfected adult men and women between the ages 18 to 50 years, inclusive. A target of 150 subjects will participate in this study with 25 subjects in Group 1, 100 subjects in Group 2, and 25 subjects in Group 3 (see table below). Group 1 represents the "base-case" regimen which allows bridging of data from this study to study VAC89220HPX2004. Randomization will be stratified by region. Subjects will receive intramuscular (IM) doses of study vaccine or placebo at 4 time points: Ad26.Mos4.HIV or placebo will be given at Weeks 0 and 12; Ad26.Mos4.HIV together with either Clade C gp140 plus adjuvant or a combination of Mosaic and Clade C gp140 plus adjuvant, or placebo will be given at Weeks 24 and 48.

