6. DOSAGE AND ADMINISTRATION

During the main study, each subject will receive doses of study vaccine or placebo at 4 time points according to randomization, on Weeks 0, 12, 24, and 48, administered by IM injection into the deltoid. Subjects eligible and consenting for the late boost vaccination will receive an additional dose of Ad26.Mos4.HIV in combination with bivalent gp140 or placebo at Week 192 -4 weeks/+ 4 months (ie, approximately 3 years after the 4th vaccination of the primary vaccination series).

For visits with only one injection (ie, at Week 0 and 12), preferably the deltoid of the non-dominant upper arm is used. When 2 injections are to be given at one visit (ie, at Week 24, 48 and late boost vaccination), it is required to use a different deltoid for each injection. Two injections in the same deltoid are allowed only if medically indicated.

For information on vaccination windows, see Section 9.1.2. If a subject cannot be vaccinated within the allowed window, then that vaccination should not be administered. However, if the window is missed due to a study pause (see Section 11.9), vaccination will be assessed on a case-by-case basis, upon discussion between sponsor and investigator. If a subject misses more than one study vaccination, he/she will be withdrawn from further study vaccination (see Section 10.2).

Table 3: Description of Interventions					
Test articles	Ad26.Mos4.HIV	Clade C gp140 with aluminum phosphate	Clade C gp140 + Mosaic gp140 with aluminum phosphate*	gp140 HIV bivalent vaccine*	Placebo
Description	See Section Vaccine Information.				
Dose/delivery (0.5 mL injection)	5x10 ¹⁰ viral particle (vp)	250 mcg Clade C gp140, mixed with aluminum phosphate adjuvant (0.425 mg aluminum)	125 mcg Clade C gp140 + 125 mcg Mosaic gp140, mixed with aluminum phosphate adjuvant (0.425 mg aluminum)	80 mcg Clade C gp140/75 mcg Mosaic gp140/ aluminum phosphate adjuvant (425 mcg aluminum)	0.9% saline
Frequency	Week 0, 12, 24, 48, and Week 192** (if applicable)	Week 24 and 48	Week 24 and 48	Week 192** (if applicable)	Week 0, 12, 24, 48, and Week 192** (if applicable)
Delivery method	IM in deltoid	IM in deltoid	IM in deltoid	IM in deltoid	IM in deltoid
Delivery instructions		Refer to the St	udy Procedures Mai	nual for details.	

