**DEFINITION OF TERMS**

Randomization	1:4:1 ratio			
Study vaccine	
 
- Ad26.Mos4.HIV (Ad26.Mos.1.Env + Ad26.Mos.2.Env + Ad26.Mos1.Gag-Pol + Ad26.Mos2.Gag-Pol): Total dose is <math>5 \times 10^{10}</math> viral particles (vp) per 0.5 mL injection
 
- Clade C gp140 DP: gp140 DP with 250 mcg total protein, mixed with aluminum phosphate adjuvant (0.425 mg aluminum) at the pharmacy, per 0.5 mL injection
 
- Clade C + Mosaic gp140 DP: a combination of Mosaic gp140 [125 mcg] and Clade C gp140 [125 mcg], mixed with aluminum phosphate adjuvant (0.425 mg aluminum) at the pharmacy, per 0.5 mL injection
 
- Placebo: 0.9% saline, 0.5 mL injection
 
			
Vaccination compliance	Each vaccine administered (if applicable) according to planned schedule			
Vaccine regimen	Group	Planned N	Day 1, Week 12	Week 24, Week 48
	1	25	Ad26.Mos4.HIV	Ad26.Mos4.HIV + Clade C gp140
	2	100	Ad26.Mos4.HIV	Ad26.Mos4.HIV + Clade C + Mosaic gp140
	3	25	Placebo	Placebo + Placebo

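### In the by-vaccine safety tables, the placebo local rate at two-injection visits covers both arms while each vaccine's covers one, and the per-dose unit is undefined for placebo

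*SAP*

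**What the plan says.** SAP section 5 tabulates safety per period by regimen. For a selection of adverse event and laboratory tables it adds two by-vaccine presentations:

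- **Per subject by vaccine.** A subject counts once per event and period. "The denominator is the number of subjects that received the considered vaccine in the considered period".
- **Per dose by vaccine.** The "numerator is the sum of post-dose 1, 2, 3 and 4 events" is taken from the per-subject table. "The denominator is the total number of doses administered of the considered vaccine over all subjects".

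For visits with two injections, SAP section 5 states: "The local solicited events should be linked to the medication injected in that specific injection site". If the site is unknown, the event is credited to both products the subject received. Systemic and unsolicited events are always credited to both. The only worked example pairs Ad26 with gp140. No passage says how two injections of the same product at one visit are counted.

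Group 3 gets one placebo injection at each of Weeks 0 and 12 and two at each of Weeks 24 and 48 (SAP Definition of Terms; Protocol Table 1). On two-injection visits, Protocol section 6 says "it is required to use a different deltoid for each injection", with an exception only for medical reasons. Planned sizes are "25 subjects in Group 1, 100 subjects in Group 2, and 25 subjects in Group 3" (Protocol Synopsis and section 3.1). The late-boost control is also two placebo injections at one visit (Protocol Table 2), and the SAP names the late boost in its linking rule.

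**The concern.** Solicited local and systemic events are primary endpoints (Protocol section 2.1), and Group 3 is the only concurrent control in the main study. A reader who wants the reactogenicity of one product against saline will go to the by-vaccine tables. There, site linking separates Ad26 from gp140 in an active subject, but both arms of a placebo subject lead to the same product. The placebo local rate then rests on twice as many injection sites per visit as either vaccine rate, and the apparent vaccine excess shrinks.

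The per-dose table raises a second question. Its numerator allows at most one count per subject, event and period. If its denominator counts injections, placebo is the only product for which numerator and denominator have different units.

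**Working it through.** The documents give no placebo rate and no dose total, so there is no stated figure to reproduce. Group sizes and schedule come from the documents. The per-arm and per-visit event rates below are assumptions, and full completion is assumed.

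**1. Local events, per-subject table, after doses 3 and 4**

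Let p be the per-arm rate, the same for saline and vaccine. A vaccine shows p. Placebo shows the chance of a reaction in at least one of two arms:

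- independent arms: 1 − (1 − p)²
- perfectly correlated arms: p

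| Assumed p | Vaccine shows | Placebo, correlated | Placebo, independent | Ratio, independent |
|---|---|---|---|---|
| 5% | 5% | 5% | 9.75% | 1.95 |
| 10% | 10% | 10% | 19% | 1.9 |
| 20% | 20% | 20% | 36% | 1.8 |
| 30% | 30% | 30% | 51% | 1.7 |

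This does not depend on what a dose is. Doses 1 and 2 compare one injection with one and are unaffected.

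**2. Per-dose table: largest possible numerator over denominator**

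A placebo completer has 1 + 1 + 2 + 2 = 6 injections over 4 visits.

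| Product | Largest numerator | Injections | Visits at which given |
|---|---|---|---|
| Placebo | 25 × 4 = 100 | 25 × 6 = 150 | 100 |
| Ad26.Mos4.HIV | 125 × 4 = 500 | 500 | 500 |
| Clade C gp140 | 25 × 2 = 50 | 50 | 50 |
| Clade C + Mosaic gp140 | 100 × 2 = 200 | 200 | 200 |

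Counting injections gives placebo a ceiling of 100/150 = 66.7%; every other product can reach 100%. A systemic event with a true per-visit rate r would show as 4r/6, so 10%, 20% and 30% become 6.7%, 13.3% and 20.0%. Counting visits gives 100/100 and no dilution.

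**3. Why choosing one unit for all events is not enough**

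Take local events per dose at p = 10%, where Ad26 shows 10%.

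- Independent arms, visits: (0.10 + 0.10 + 0.19 + 0.19)/4 = 14.5%
- Independent arms, injections: 0.58/6 = 9.7%
- Perfectly correlated arms: 10% by visits, 0.40/6 = 6.7% by injections

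A visit denominator is right for systemic events but can leave local events inflated. An injection denominator roughly repairs local events if the arms are independent, but dilutes systemic events.

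**The case against.** The best counter-argument is that a fair comparison is already planned. The by-regimen tables set a reaction in either arm of an active subject beside a reaction in either arm of a placebo subject, and the late-boost period is reported for the two late-boost regimens in the same way. The by-vaccine tables are supplementary. Safety is descriptive (Protocol section 11.5), and the pausing rules in Protocol section 11.9 use individual events and counts of similar events, not placebo rates. All of this stands. A reader might infer that the trial's main vaccine-placebo safety comparison is biased; the documents do not support that.

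A reader might also infer that placebo per-dose rates will be divided by six. The SAP's own usage points the other way: its phase and period table (section 2.1) treats Dose 3 and Dose 4 as single doses, each made of two injections. Protocol Table 3 and the SAP's placebo definition do describe the product per 0.5 mL injection, so the unit is open, but a six-fold denominator is a possibility and not a stated rule. For the same reason the documents do not establish that systemic excess is overstated per dose.

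Nor is near-doubling of the local rate established. Two arms of one person, recorded in one diary, may well react together, and with perfect correlation there is no inflation. Where the site link is missing, active events are credited to both products, which narrows the gap further.

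Finally, SAP section 1 says outputs up to Week 72 will not be repeated, so part of this concerns completed tables. That affects how to act, not whether the rates are comparable.

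**Conclusion.** The local-event point holds on the text. With site linking, two placebo injections in different deltoids and a count of subjects per product, the by-vaccine placebo local rate after doses 3 and 4 is an either-arm rate beside one-arm rates for Ad26 and gp140. The same applies at the late boost wherever it is tabulated by vaccine. The inflation factor lies between 1.0 and about 1.9, depending on the correlation between arms and on the per-arm rate, neither of which the documents give. Any inflation understates each vaccine's local excess in these tables.

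The per-dose point is an undefined unit. On the reading that the SAP's usage favours there is no bias; on the injection reading, placebo systemic and unsolicited rates are cut by one third. Both points are confined to supplementary, descriptive tables.

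**What to change.** In SAP section 5:

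1. For systemic and unsolicited events, state that a dose is a vaccination visit, so a placebo completer of the main study contributes 4.
2. For local solicited events in by-vaccine tables, count injection sites in both numerator and denominator for every product. For placebo the largest local count is then 150 over 150 sites. Alternatively, show placebo at two-injection visits only beside either-arm active rates.

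Apply this to late-boost and any future outputs. Add a footnote to the completed Week 72 by-vaccine tables saying that placebo local rates after doses 3 and 4 cover two arms, and which unit the per-dose denominator used. The cost is a few sentences, minor reprogramming and the footnote; no new data are needed.
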